2.3.3. Exploratory Efficacy Outcome Measures

For exploratory outcome measures see Appendix 1.

2.3.4. Pharmacokinetic Outcome Measures

- Population and individual primary PK parameter estimations (e.g., clearance and volume of distribution) and the influence of various covariates on these parameters.
- Secondary PK parameters (e.g., AUC, C_{trough}) derived from the individual post-hoc predictions.

2.3.5. Safety Outcome Measures

- Changes in safety laboratory tests (hematology, chemistry and coagulation) from baseline over time.
- Incidence of treatment-emergent abnormal laboratory values and abnormal laboratory values reported as AEs.
- Incidence and severity of AEs.
- Incidence of ADAs.
- Changes in ECG assessments from baseline over time; incidence of abnormal ECG assessments.
- Change in blood pressure (BP [systolic and diastolic], heart rate, and orthostatic measurement from baseline over time, incidence of abnormal blood pressure [systolic and diastolic], heart rate, and orthostatic changes).
- Incidence of exacerbation of motor and psychiatric side-effects.
- Incidence of MRI abnormalities
- Incidence of infusion related reactions (IRR)
- Summary of CSSR-S

2.4. DETERMINATION OF SAMPLE SIZE

The sample size calculations were aimed to power the study for the primary endpoint of change in total MDS-UPDRS (sum of Parts I, II and III) at Week 52, see Section 4.7.2 for a full description of the endpoint.

A sample size of 100 randomized participants per group (300 participants for the three groups) was chosen to obtain a power of approximately 80% at two-sided α -level of 20% for the comparison of each active dose arm to placebo. The power calculation was based on simulations of the mixed-effect model repeated measures (MMRM) analysis

planned for the primary efficacy variable. Assessments performed while on any symptomatic treatment started after randomization will not be included in the analysis. The following assumptions were made for simulating the data:

- Seven post-baseline assessment visits,
- An overall rate of missing values (due to participants starting symptomatic therapy or prematurely withdrawing from study medication during the 52-week placebo-controlled treatment period) of 25% in the placebo group and 20% in each dose group at Week 52, with incremental rates over the 52-week placebo-controlled period
- A linear mean increase of the primary endpoint (natural progression) of eight points/year for the placebo arm, with a linearly increasing common standard deviation reaching nine points at Week 52
- An effect size of 0.33 (difference=3 points, relative reduction of progression=37.5%) for one dose group versus placebo at Week 52 with increasing magnitude of treatment difference over the placebo-controlled period
- A compound symmetry correlation structure assuming a correlation coefficient of 0.55 between different visits.

Table 1 provides the additional information needed to perform the simulations.

Table 1. Assumptions Used for Simulations

Post-Baseline Visit (weeks)	8	16	24	32	40	48	52
Change from baseline in MDS-UPDRS total (sum of Parts I, II, and III), placebo arm (points)	1.2	2.4	4	4.8	6	7.2	8
Change from baseline in MDS-UPDRS total (sum of Parts I, II, and III), active treatment arm (points)	0.8	1.5	2.5	3.0	3.8	4.5	5
Common standard deviation for change from baseline in MDS UPDRS total (points)	6.75	7.25	7.75	8	8.5	8.75	9
Percentage of patients with non-evaluable data, placebo*	1%	3%	5%	7%	17%	22%	25%
Percentage of patients with non-evaluable data, treatment*	1%	3%	5%	7%	12%	17%	20%

*Includes data from patients that prematurely dropped out from the study and/or started symptomatic therapy after randomization.

The assumptions on progression, variability, dropout rate and likelihood to start symptomatic therapy within the first 52 weeks of treatment, with or without a MAO-B inhibitor as background therapy, were derived from analyses based on the Parkinson's Progression Markers Initiative (PPMI) database and various sources of information from the literature.

The sample size of 100 patients per arm also provides 76% power ($\alpha=20\%$, two-sided) to reject the null hypothesis assuming a 37.5% reduction (or assuming an effect size=0.31 based on assumption of decline over 52 weeks of 0.157 for the placebo arm and standard deviation of 0.185 derived from the PPMI database) for the key secondary endpoint, the DaT-SPECT signal loss at Week 52, for the pairwise comparison of each active dose arm to placebo. The missing values assumption used was 15% and included participants who withdrew from study medication before Week 52 or who did not have a valid DaT-SPECT assessment at Week 52. Assessments performed while on any symptomatic treatment started after randomization will not be excluded from the analysis.

No adjustments for multiple comparisons will be incorporated into the analyses.

The protocol stated that the sample size could have been adjusted depending on the outcome of the iDMC review performed during the study. If the enrollment to the high dose is stopped and a new dose is introduced as advised by the iDMC, the Sponsor could have proposed enrolment of (up to) an additional 20% of patients. The aim of this increase in sample size would have been to ensure a power of approximately 80% at two-sided α -level of 20% (corresponding to a one-sided α -level of 10%) for the pairwise comparison of the new dose arm to the placebo group consisting of participants randomized after the decision to include the new dose arm.

The sample size could have been adjusted if the initial assumptions on dropout rate and likelihood to start symptomatic PD treatment as described in Table 4 were different from the actual values observed. If that was the case, the Sponsor could have increased enrolment up to 20% of the total sample size. The aim of this increase in sample size was to ensure that the pairwise comparison of each active dose arm to placebo remained adequately powered.

2.5. ANALYSIS TIMING

The following analyses were planned for this study

Table 2. Analyses Timings

Analysis	Timing of Analysis
First Safety interim	30 participants (approximately 10 participants per arm) have received three infusions
Second Safety interim	60 participants (approximately 20 participants per arm) have received three infusions
Part 1	all active participants have completed the Week 52 visit (Part 1: placebo-controlled, double-blind treatment period)
Part 2	all active participants have completed the follow-up visit, up to 12 weeks after cessation of treatment (regardless of whether cessation of treatment occurs at the end of or during Part 1 or Part 2)

2.6. DATA INCLUDED IN 52-WEEK DATA CUT (PART 1 ANALYSIS)

The analysis of Part 1 will take place once all the randomized patients in the study have reached the Week 52 visit or withdrawn from the study prior to Week 52; all data from the study are in the database, and the database is frozen. The patient data will be cut at the day prior to the Week 56 visit. All data prior to this cut-off will be cleaned and verified for completeness to the best extent possible.

The following data will be included in the 52-week data cut: all screening and post-baseline data with a clinical date (i.e., administration/assessment/onset/start date) the day before the date of re-randomization to Part 2 (Week 56) will be included.

The Part 1 data cut will include all data regardless of the type of study visit at which it was collected. This may include data collected at prior to start dopaminergic visits, unscheduled visits, dosing termination visits, early termination visits, or safety follow-up visits, if the visit date was before re-randomization to Part 2 (Week 56).

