### **5.3.5.3 Persistent or Recurrent Adverse Events**

A persistent adverse event is one that extends continuously, without resolution, between patient evaluation time-points. Such events should only be recorded once on the Adverse Event eCRF. The initial severity of the event should be recorded, and the severity should be updated to reflect the most extreme severity any time the event worsens. If the event becomes serious, the Adverse Event eCRF should be updated to reflect this.

A recurrent adverse event is one that resolves between patient evaluation time-points and subsequently recurs. Each recurrence of an adverse event should be recorded separately on the Adverse Event eCRF.

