4.9. SAFETY ANALYSES

All safety analyses will be based on the safety analysis population, defined in Section 4.1.4. Safety will be assessed through the summary of adverse events, laboratory test results (hematology and serum chemistry), ECG findings, and vital signs. Safety summaries for the 52-week period in Part 1 will include outcomes as described in Section 2.6.

The incidence of antibodies against prasinezumab (ADAs) will be summarized using the immunogenicity population (Section 4.1.5).

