4.9.2. Adverse Events

Verbatim descriptions of treatment-emergent adverse events will be coded using the latest version of MedDRA in effect at the time of database freeze. A treatment-emergent adverse event is defined as any new adverse event or any worsening of an existing condition with an onset date on or after the first study drug administration date.

Summaries of treatment-emergent events will be provided for each of the following categories:

- Incidence of adverse events
- Incidence of adverse events by intensity
- Incidence of adverse events by relationship to study medication
- Incidence of serious adverse events
- Incidence of adverse events leading to discontinuation of study treatment
- Incidence of adverse events of special interest
- Incidence of infusion related reactions

- C-SSR will be reported by visit

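### Part 1 adverse events are selected by onset date but can carry a severity or seriousness reached in Part 2, so worsening on active drug can be tabulated under placebo

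*SAP*

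**What the plan says.** **Which records enter.** SAP 2.6 takes "all screening and post-baseline data with a clinical date (i.e., administration/assessment/onset/start date) the day before the date of re-randomization to Part 2". The sentence lacks a word such as up to, and I read it as on or before that day. For an adverse event the relevant date is onset or start. The same section states the aim: "The patient data will be cut at the day prior to the Week 56 visit". SAP 4.9 ties the tables to this cut: "Safety summaries for the 52-week period in Part 1 will include outcomes as described in Section 2.6".

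**When the cut is taken.** The analysis runs "once all the randomized patients in the study have reached the Week 52 visit or withdrawn from the study prior to Week 52". Under SAP 2.2, participants randomized to placebo who enter Part 2 are all re-randomized to one of the two active doses.

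**How an event is recorded.** For a persistent event, Protocol 5.3.5.3 says "Such events should only be recorded once on the Adverse Event eCRF". The initial severity is entered, and then "the severity should be updated to reflect the most extreme severity any time the event worsens". It adds: "If the event becomes serious, the Adverse Event eCRF should be updated to reflect this". Protocol 5.3.5.4 and 5.3.5.5 apply the same updating to laboratory and vital-sign abnormalities.

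**What is tabulated.** SAP 4.9.2 defines a treatment-emergent event as "any new adverse event or any worsening of an existing condition with an onset date on or after the first study drug administration date". It plans incidence tables by intensity, by relationship, for serious events and for events leading to discontinuation of study treatment. It does not say as of which date those attributes are read.

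**The concern.** The cut acts on whole records through one date, while the fields that drive the severity and seriousness tables can change after that date. Consider a hypothetical placebo patient with mild back pain from Week 40 that has not resolved at Week 56. After the switch to active drug it becomes severe and leads to hospitalization at Week 70. If the database is frozen after that, the single record has a Week 40 onset, a severe grade and a serious flag. By onset date it belongs to Part 1, and by randomized arm it is a placebo event.

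Part 1 is the only period with a concurrent placebo group, and SAP Section 1 says the analyses in its main body inform the design of Phase 3. Where severe or serious events are few, one or two misattributed cases can change how the table reads.

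**Working it through.** The plan gives no figure on this point, so there is nothing to reproduce. The check traces the rules, then asks how many patients are exposed to the problem.

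**1. Does any rule break the chain?**
- *SAP 2.6, cut on the day before Week 56:* this states the intent. The only operational rule admits records by clinical date and does not restore a field to its value on that day.
- *SAP 4.9.2, treatment-emergent definition:* worsening still needs an onset date. Its only time bound is the first dose in the study, not the first Part 2 dose.
- *Protocol 5.3.5.8, preexisting conditions:* these are conditions present at screening. An event that began in Part 1 is not one, so its worsening in Part 2 gets no new entry by this route.
- *SAP 4.1.4, treatment actually received:* this handles patients given a randomized treatment other than their own. It does not move later worsening of a Part 1 event to the Part 2 treatment.

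None of these breaks it. The intensity and serious-event tables are affected directly. The relationship and discontinuation tables may be, but Protocol 5.3.5.3 describes overwriting only for severity and seriousness.

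**2. Are patients already in Part 2 at the freeze?**
SAP 3.2.1 places the two safety meetings on 8 May and 22 June 2018, after about 30 and 60 participants had three infusions. The third infusion is Day 56 and Week 56 is Day 392 (Protocol Appendices 1 and 2).
- First 30: Day 1 no later than 8 May 2018 − 55 days = 14 March 2018. Week 56 by + 391 days = 9 April 2019, ignoring visit windows.
- First 60: Day 1 no later than 28 April 2018. Week 56 by 24 May 2019.

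Protocol 1.3.2 reports a blinded review of 316 participants as of 29 November 2019. If the Part 1 freeze was no earlier (an inference; the documents do not date it), those still on treatment had at least 234/7 ≈ 33 weeks and 189/7 = 27 weeks of Part 2 time. At 1:1:1, about 10 of the first 30 and 20 of the first 60 started on placebo.

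More generally, assume uniform enrolment over S weeks and a freeze at the last patient's Week 52. The share of continuing patients past Week 56 is (S − 4)/S:

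| S (assumed) | Share past Week 56 | Longest Part 2 time |
|---|---|---|
| 26 weeks | 22/26 = 85% | 22 weeks |
| 52 weeks | 48/52 = 92% | 48 weeks |
| 78 weeks | 74/78 = 95% | 74 weeks |

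**3. How many placebo patients?**
Count = placebo N × share entering Part 2 × share with an event ongoing at Week 56 × share of those becoming severe or serious before the freeze. N = 100 is the planned arm size (SAP 2.4). The three rates are assumptions with no source in the documents.
- Low: 100 × 0.80 × 0.30 × 0.01 = 0.24
- Middle: 100 × 0.80 × 0.60 × 0.05 = 2.4
- High: 100 × 0.95 × 0.60 × 0.10 = 5.7

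**4. Which way does the comparison move?**
Write *a* for the share of an arm with an ongoing event and *w* for the share of those that worsen. Carry-back changes the active-minus-placebo difference by a(active) × w(active) − a(placebo) × w(placebo). The documents give none of these, so the sign is unknown.

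**The case against.** The strongest reply is that SAP 2.6 plainly means to exclude data from Week 56 onward and that programming could achieve this. The initial severity is recorded, and serious events have their own report with follow-up (Protocol 5.4), so the date of becoming serious may be recoverable. That stands as a reason why the fix is feasible. It does not remove the point: no analysis rule tells the programmer to use those dates, and the documents describe no dated history of grades.

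It is also fair that the scope is narrow. An event must start in Part 1, be unresolved at Week 56 and worsen before the freeze. Recurrences after resolution are separate records (Protocol 5.3.5.3), as are medically significant secondary events separated in time (5.3.5.2). A reaction to a Part 2 infusion has a Part 2 onset and falls outside the cut. The safety analyses are descriptive, and no test depends on them.

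A reader might infer two stronger conclusions, and neither is supported. The first is that the error favours the drug. Active-arm events carry Part 2 worsening back as well. A bias in favour of the drug would need carry-back to be larger in the placebo arm, and nothing in the documents shows that. The second is that the worsening disappears from the active-drug record. Part 2 analyses are left to a later SAP version or a separate SAP (SAP Section 1 and 4.1.6), which can still count it.

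**Conclusion.** The rule is wrong as written. Followed literally, it places intensity and seriousness reached in Part 2 in the Part 1 tables, and for placebo patients that worsening occurred on active drug. This is more than a missing detail, because two explicit rules combine to give the misattribution.

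The conclusion does not extend to a direction of bias or to loss of events from Part 2. The number of placebo patients is probably small. The range of about 0.2 to 6 per 100 rests entirely on assumed rates and should not be quoted as an estimate. That many patients are past Week 56 at the freeze is better supported: it follows from the freeze rule and the meeting dates, although the enrolment span and freeze date are not stated.

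**What to change.** In SAP 2.6 and 4.9.2, state that Part 1 tables use the worst intensity, and the seriousness and action taken, with a clinical date before the first Part 2 infusion. The sources should be dated grade changes, the date of becoming serious in the serious adverse event report, and the date of drug discontinuation.

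Use the eCRF audit trail only to find records changed after Week 56 for review, including changes to relationship. It should not supply the values. It logs time of entry (Protocol 7.2), so a Week 50 worsening entered after Week 56 would be wrongly dropped from Part 1.

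List the events ongoing at Week 56 whose grade or seriousness changed afterwards, by arm. In the Part 2 SAP, count such worsening as treatment-emergent under the Part 2 treatment.

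Do not ask sites to open a new record for the worsening unless Protocol 5.3.5.3 is reconciled with that, since it requires a single record.

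The cost is a few sentences in the SAP and a modest extract and review of events ongoing at Week 56. If the eCRF holds no dated grades, that review will need queries to sites. Patients have no added burden.

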3. STUDY CONDUCT

3.1. RANDOMIZATION ISSUES

Randomization was done via an Interactive Voice/Web Response System (IxRS). Patients were randomized once all screening assessments had been completed and eligibility confirmed.

For Part 2, participants who complete the initial placebo-controlled part of the study (Part 1) and fulfil the criteria described in section 2.2 enter the extension part of the study (Part 2), in which case, a re-randomization will take place. Although only placebo patients will be re-randomized at the start of Part 2, see section 2.2, all patients will be registered in IxRS at the start of Part 2 to ensure the blind is maintained.

Both randomization lists were generated by the IxRS provider.

Note to file 29, found in eTMF system, was written to clarify when the correction of entry errors in IxRS for 'prior background therapy with MAO-B inhibitors' and/or 'Dopaminergic therapy since start of the study' is allowed. If an entry error in Part 1 is made regarding prior background therapy with MAO-B inhibitor, then the Sponsor will not allow a change in the IxRS as this variable is a stratification factor. If an entry error is made regarding the start of symptomatic PD therapy since the start of the study, the Sponsor will allow a change in IxRS since this item is not a stratification factor in Part 1; these changes are only allowed to be made before the patient is re-randomized at week 56.

The stratification factors to use in the analysis will be the ones obtained in the IxRS. A cross tabulation will be created to assess discrepancies between the IxRS stratification factors and the ones derived with the eCRF data.

3.2. DATA MONITORING

3.2.1. INDEPENDENT DATA MONITORING COMMITTEE

This study utilizes an independent Data Monitoring Committee (iDMC), which monitors safety of the study. There were two scheduled safety iDMC meetings: after approximately 30 participants (approximately 10 participants per arm) and 60 participants (approximately 20 participants per arm), respectively, received their first three infusions. The first meeting happened on 8th May 2018 and the second on 22nd June 2018. For both meetings the analyses of the safety data were conducted by an external statistical group and reviewed by the iDMC. The iDMC was unblinded at the aggregate and individual level to review and evaluate safety data. Interactions between the iDMC and the Sponsor were carried out as specified in the iDMC Charter. Sponsor personnel did not have access to the results of these data analyses.

The iDMC may be convened at additional time-points if warranted by safety considerations or for other reasons until the study is unblinded to the sponsor, end of Part 1 of the study (for further details see the separate iDMC Charter).

4. STATISTICAL METHODS

4.1. ANALYSIS POPULATIONS

4.1.1. Modified Intent-to-treat Population

The modified intent-to-treat (mITT) population will include all patients randomized in the study who received any amount of study drug treatment. Analyses based on the mITT population will be based on the treatment arm the patient was randomized.

4.1.2. Per Protocol Population

A Per Protocol (PP) population will not be defined.

4.1.3. Pharmacokinetic Analysis Population

Any subjects with at least one adequately documented PK measurement will be included in the PK Analysis Population. Any exclusion of such a subject will be documented together with the reason for exclusion.

4.1.4. Safety Analysis Population

All randomized participants receiving any dose of the study drug will be included in the safety analysis. Patients who received any randomized treatment other than that to which they were randomized will be analyzed according to the treatment actually received.

4.1.5. Immunogenicity Analysis Population

Participants who had at least one pre-dose and one post-dose ADA assessment will be included and analyzed according to the prasinezumab dose they actually received. Only samples from prasinezumab-treated participants will be analyzed.

4.1.6. Part 2 (Extension) Population

Participants who complete the double-blind, placebo-controlled treatment period (Part 1) will continue in an all-participants-on- prasinezumab treatment (high or low dose) for an additional 52 weeks (Part 2), but will be blinded to prasinezumab dose. This will allow collection of safety information on long-term exposure with prasinezumab, as well as concomitant dopaminergic treatment. Analyses for Part 2 will be described in a future version of the SAP.

4.2. DEFINITION OF BASELINE

Baseline for the MDS-UPDRS

Baseline for the MDS-UPDRS will be considered as the last time point before treatment when the three parts (I, II, and III) are non-missing following the rules stated in Section 4.7.2.1.

Definition of Baseline for Statistical Analyses

Baseline will be defined as last available pretreatment value taken on or before the day of first treatment dose and will be used in summaries of demographic characteristics as well as any change from baseline analyses of efficacy, and safety.

For endpoints defined in terms of change from baseline, patients who do not have a pretreatment value reported for a particular assessment (if any) will be excluded from the change from baseline analyses for that assessment.

